9.4 Statistical Analyses

9.4.1 General Approach

Descriptive statistics will be presented as percentages for binary variables, and as means with standard deviations or median with IQR depending on the distribution of the data. For inferential tests, the Type I error will be set at 0.05 using two-tailed tests. Covariates will be determined based on their significance as independent predictors of outcome, although age and sex will be included in all models. Check on normality will be performed through data visualization as well as using appropriate statistical tests of normality (eg Shapiro-Wilks test). Transformation of non-normally distributed continuous variables will be performed, and models will be compared to non-transformed models using non-parametric tests.

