9 STATISTICAL CONSIDERATIONS

9.1 Statistical Hypotheses

The primary hypotheses are: (1) Scores on the Genetics Knowledge Scale (GKS) will not differ between virtual pre-test genetic counseling and IMAGINE-PD methods, and (2) Scores on the genetic counseling satisfaction scale and test-related distress scale (IES-R) will not differ between telephone and telegenetic results disclosure methods. The primary analyses of knowledge will be measured by the GKS at 4 weeks after pre-test counseling; Satisfaction by the GCSS score between genetic counseling groups immediately after pretest and disclosure counseling; and test-related distress by the IES-R score at 3 months between post disclosure. The null hypothesis is that these methods differ.

Secondary hypotheses include IES-R at 6 months between genetic counseling groups, scores on affect, outcomes, and quality of life scales at 3 and 6 months.

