9.2 Sample Size Determination

The difference in IES-R between groups after genetic disclosure counseling is used to determine sample size. A clinically significant difference in IES-R score is not defined. Sample size is determined from previously reported normative data of the IES-R in a community sample of N=154 non-PTSD ex-service members, demonstrating a mean of 1.82 (SD=1.05).¹⁶ A range of equivalence limits, the difference in standard deviation beyond which a significant difference would be considered relevant, are demonstrated in **Table 3** at alpha = 0.05 and power of 80%.²⁵ A sample size of N=80/counseling group (divided between PD+gene+ (45%), PD+gene- (45%), and

PD-gene+ groups (10%)), with an expected attrition of 15-20%, would allow for analysis of the primary outcome at a conservative 0.5-0.75 SD equivalence limit, and allow genetic and PD-subgroup analysis.

8		8
Equivalence limit (SD)	Per Group	Total Sample Size
0.5	80	320
0.75	36	132
1	20	80

Table 3. Sample Size Estimates.

9.3 **Populations for Analyses**

Analyses will be conducted for all randomized participants *in the* Intention-to-Treat (ITT) Analysis Dataset, as well as the Per-Protocol Analysis Dataset defined a subset of the participants in the full analysis (ITT) set who complied with the protocol sufficiently to ensure that these data would be likely to represent the effects of study intervention according to the underlying scientific model (e.g., participants who complete the 3-month study visit).

Protocol 843748-
GET VIRTUAL PD
IMAGINE-PD

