9.4.2 Analysis of the Primary Efficacy Endpoint(s)

The primary endpoint is the score on the IES-R scale, which will be treated as a continuous variable. The primary outcome will be difference in IES-R score between the counseling groups at 3 months post disclosure. A linear regression model accounting for baseline differences in age, sex, and other relevant covariates will be used. Missing data will be handled in 2 ways: an analysis of available data, and using an imputed dataset. Imputation will be performed via multiple imputation using the MICE (Multivariate Imputation via Chained Equations) package. Imputation in this package uses linear and logistic regression to predict missing values. MICE assumes missing values are missing at random, and overall missingness pattern will be assessed using this package. Results will be reported as means with standard errors. Assumptions for each statistical model will be tested. Results will be analyzed using 2 approaches: data transformation and using nonparametric statistical tests, where necessary. Bonferroni correction will be used to correct for multiple-testing comparisons.

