9.4.3 Analysis of the Secondary Endpoint(s)

All secondary outcome variables will be treated as continuous variables. The hypotheses will be difference between counseling method groups at all study timepoints. A linear regression model accounting for baseline differences in age, sex, and other relevant covariates will be used. Missing data will be handled in 2 ways: an analysis of available data, and using an imputed dataset. Results will be reported as means with standard errors. Assumptions for each statistical model will be tested. Results will be analyzed using 2 approaches: data transformation and using nonparametric statistical tests, where necessary. Bonferroni correction will be used to correct for multiple-testing comparisons.

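### The trial aims at equivalence, but section 9.4 states no criterion for concluding it, so the null hypothesis in 9.1 has no specified test

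*Combined protocol and SAP*

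**What the plan says.** The synopsis, 4.1 and 4.2 all state an equivalence aim, although 4.1 also labels the design non-inferiority. Section 9.1 expects, for example, that satisfaction and distress scores "will not differ between telephone and telegenetic results disclosure methods", and adds: "The null hypothesis is that these methods differ". Section 9.2 sizes the trial on equivalence limits for IES-R. It says "A clinically significant difference in IES-R score is not defined" and gives the limit as a range of 0.5-0.75 SD.

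The analysis sections do not carry this forward:

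- 9.4.1: "For inferential tests, the Type I error will be set at 0.05 using two-tailed tests".
- 9.4.2: "The primary outcome will be difference in IES-R score between the counseling groups at 3 months post disclosure". The model is a linear regression, results are reported as means with standard errors, and "Bonferroni correction will be used to correct for multiple-testing comparisons".
- 9.4.3, for secondary outcomes: "The hypotheses will be difference between counseling method groups at all study timepoints".

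The number of primary tests also varies. Section 9.4.2 names one endpoint, the hypothesis in 4.1 two, and the synopsis and section 3 three. Section 9.1 could make four, because it measures "Satisfaction by the GCSS score between genetic counseling groups immediately after pretest and disclosure counseling".

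**The concern.** An equivalence-type null is rejected only by showing that the difference lies inside a stated margin. Section 9.4 contains no margin, no two one-sided tests (TOST), no CI compared with a limit, and no other criterion. A non-significant difference does not show equivalence. A significant one can still lie inside the limit that 9.2 treats as not relevant. The plan does not say how either result would be read.

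For the Genetics Knowledge Scale (GKS) and the Genetic Counseling Satisfaction Scale (GCSS) no margin exists anywhere. For IES-R a range is given but no single value. Section 9.4.2 speaks only of counseling groups, so it does not say whether the term tested is the pooled factorial main effect or a comparison of single cells. What is at stake is how every primary conclusion is reached.

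**Working it through.** **Inputs.** From 9.2: 80 per group, 320 in total, attrition 15-20%, limits 0.5 and 0.75 SD, SD 1.05, alpha 0.05, power 80%. From 6.4: 1:1:1:1 allocation. A pooled arm is two groups: 160 × 0.80 = 128 to 160 × 0.85 = 136. A cell is 80 × 0.80 = 64 to 80 × 0.85 = 68. Section 7.2 provides for replacement, so 160 per arm and 80 per cell are also shown. Calculations are in SD units, unadjusted, with equal variances.

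**Reproducing Table 3 (0.5 SD row, 80 per group).**

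- TOST with zero true difference: n = 2 × ((1.645 + 1.282)/0.5)² = 68.5, so 69. Then 69 × 1.15 = 79.4, so 80 (69/0.85 gives 82).
- Ordinary two-sided difference test: n = 2 × ((1.960 + 0.842)/0.5)² = 62.8, so 63, or 64 with the t distribution. Then 64/0.80 = 80.

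Both routes reach 80, so Table 3 does not reveal which test was intended.

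**Where the two rules collide (pooled, single test).** The smallest significant observed difference is t(0.975) × √(2/n). The largest observed difference at which a 90% CI stays inside 0.5 SD is 0.5 − t(0.95) × √(2/n).

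| n per arm | Significant from | Equivalent up to |
|---|---|---|
| 128 | 1.969 × 0.1250 = 0.246 | 0.5 − 1.651 × 0.1250 = 0.294 |
| 136 | 1.969 × 0.1213 = 0.239 | 0.5 − 1.651 × 0.1213 = 0.300 |
| 160 | 1.967 × 0.1118 = 0.220 | 0.5 − 1.650 × 0.1118 = 0.316 |

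**How often both happen at a true 0.25 SD difference** (normal difference, integrated over the SD estimate). The number of tests behind the Bonferroni correction is not stated, so it is varied. Each entry is 128-136 per arm; then 160 per arm.

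| Tests | Both rules corrected | Only the difference test corrected |
|---|---|---|
| 1 | 15-20%; 33% | 15-20%; 33% |
| 2 | 0.4-1.3%; 10% | 5-9%; 22% |
| 3 | about 0%; 1.7% | 2-4%; 15% |

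**If non-significance were read as equivalence** (the plan does not say this), the chance that a true 0.5 SD difference passes, from the non-central t, is:

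| Tests | Pooled, 128-136; 160 | Cells, 64-68; 80 (sensitivity case) |
|---|---|---|
| 1 | 1.6-2.1%; 0.6% | 17.5-19.9%; 11.8% |
| 3 | 4.4-5.7%; 2.0% | 31-34%; 23% |
| 4 | 5.5-7.0%; 2.5% | not tabulated |

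TOST holds this at no more than 5% at any sample size.

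**If the margin were chosen after the data**, at a true 0.5 SD difference a 90% CI rule concludes equivalence in 5% of trials with a 0.5 SD margin and in 64-66% (72% at 160 per arm) with 0.75 SD. On the scale of the SD in 9.2 these margins are 0.5 × 1.05 = 0.53 and 0.75 × 1.05 = 0.79 points. I take that scale to be the mean-item score; 8.1 describes IES-R both as a mean of items and with an 88-point total.

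**The case against.** Four points on the other side carry weight.

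- A reader might infer that 9.4 cannot reject the null in 9.1. That goes too far. The regression estimate and its standard error are what TOST needs, a between-group difference is what any equivalence analysis estimates, and 9.4.3 concerns secondary outcomes only. What stands is that no criterion is stated.
- A reader might infer that the IES-R margin was left open for later choice. The documents do not say so. The 0.5-0.75 SD range can describe what is achievable after attrition, since 64-68 per group falls between the Table 3 rows for 80 and 36. N = 80 per group matches the 0.5 SD row. Even so, no single margin is fixed, and GKS and GCSS have none.
- A reader might infer that the plan takes a non-significant result as equivalence, and so often passes a true 0.5 SD difference. No section states that reading. On pooled arms, which fit the method contrasts in 9.1, it would pass 1.6-2.1% for one test. The larger cell figures are a sensitivity case.
- The 15-20% conflict holds only if one test is counted. That is a legitimate reading, because 9.4.2 names one primary endpoint. With three endpoints and both rules corrected, the conflict largely disappears, while the risk from reading non-significance as equivalence grows.

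None of these supplies the missing rule.

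**Conclusion.** The concern holds and should be fixed before data are seen: as written, the plan does not test its own null. The contradiction lies in the text and does not depend on the figures. Their size depends on the number of tests, on pooled or cell comparison, on how many participants are replaced, and on unadjusted equal-variance calculations. This is a fault in the decision rule. It is not evidence that the trial is too small: with a 0.5 SD margin and zero true difference, pooled TOST power for IES-R is 98-99% (99.5% at 160 per arm).

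**What to change.** In 9.4.1 and 9.4.2:

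1. State that each primary conclusion rests on the 90% CI (TOST, one-sided 0.05) for the adjusted mean difference lying wholly within plus or minus one prespecified margin.
2. Fix one IES-R margin before data are seen, naming the SD and the scoring scale. The Table 3 row that gives N = 320 is 0.5 SD. Set and justify one margin each for GKS and GCSS.
3. Name the model term as the pooled factorial main effect that matches 9.1. Reconcile the pre-test comparator: the synopsis compares IMAGINE-PD with telephone, whereas the arms in 4.1, and 4.2 and 9.1, compare it with virtual visits.
4. State the number of primary tests, including whether the pre-test GCSS counts, and whether each can succeed alone. Only if so, widen the CI to 1 − 2 × 0.05/k: 95% for two tests, 96.7% for three, 97.5% for four.
5. Reconcile the non-inferiority label in 4.1 with the equivalence aim.

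The cost is wording and margin justification, with no new data. The GKS and GCSS margins need real work, because both scales are to be adapted and the documents give no SD for either. With Bonferroni over two to four tests, pooled IES-R power at zero difference is 92-97% (97-99% at 160 per arm). If the true difference is 0.25 SD, it is 64-66% (72%) uncorrected, or 40-54% (49-61%) with that correction.

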4 STUDY PLAN

4.1 Study Design

The proposed study is a single-center, prospective, factorial, non-inferiority, randomized cohort design to test the equivalence of telephone genetic counseling model to novel forms of pre-test genetic counseling and telegenetic results disclosure in participants with PD carrying a *GBA* or *LRRK2* variant (PD+*gene*+), participants with PD not carrying a *GBA* or *LRRK2* variant (PD+*gene*+), participants with PD not carrying a *GBA* or *LRRK2* variant (PD+*gene*-), and a group of at-risk *LRRK2* or *GBA* variant carriers without PD (PD-*gene*+). Participants will be recruited from a single center at the University of Pennsylvania Parkinson's Disease and Movement Disorders Center. A separate biobanking protocol, called the Molecular Inegration in Neurological Diagnosis MIND Cohort (UPenn IRB # 830237) enrolls subjects with PD and collects optional consent for recontact based on eligibility for additional studies. Subjects would be recruited to GET Virtual PD after enrolling MIND and after a blood or saliva sample has been collected and research-based genetic testing has been performed, but before clinical-confirmation genetic testing. GET Virtual PD will serve as the follow study to MIND that will allow access to genetic counseling and clinical genetic confirmation testing.

Enrolled participants will be randomized into one of 4 groups based on pre- and postgenetic test counseling: (1)IMAGINE-PD/Virtual, (2)IMAGINE-PD/Telephone, (3)Virtual/Virtual, and (4)Virtual/Telephone, stratified by genetic group. They will receive pretest genetic counseling through the Interactive Multimedia Approach to Genetic counseling to INform and Educate in Parkinson's Disease (IMAGINE-PD) website or via virtual visit with a genetic counselor. Participants will be asked to complete questionnaires on genetic knowledge, cognitive and affective outcomes prior to and 4 weeks after pre-test genetic counseling. All participants will then have clinical genetics results disclosure via virtual visit or by telephone with a genetic counselor. Patient-reported cognitive and affective outcomes will be measured 6 weeks and 6 months after genetic results disclosure. The hypothesis is that performance on the genetic knowledge scale and the revised impact of events scale will be equivalent between counseling groups at 4 weeks after pretest counseling and 6 weeks post disclosure, respectively.

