6.4 Measures to Minimize Bias: Randomization and Blinding

Subjects will be randomized 1:1:1:1 into each of the 4 factorial-design groups: IMAGINE-PD/Virtual, IMAGINE-PD/Telephone, Virtual/Virtual, Virtual/Telephone. Participants and investigators will be blinded to the genetic testing results (research or clinic confirmation test) until the disclosure visit. The non-clinical researcher from the MIND study who will provide blinded lists of potential participants will not be involved in study conduct, data collection, patient interaction, or have access to any clinical data collected in the GET Virtual PD study.

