9.4.7 Sub-Group Analyses

All Primary and Secondary endpoints will be compared using age and sex as covariates in each multivariate model. PD and Gene groups will also be compared.

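### Minor, free improvement: Section 9.4.1 picks covariates by their significance against the outcome, so no primary model commits to the randomisation stratum or to the baseline scores already collected

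*Combined protocol and SAP*

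**What the plan says.** **Randomisation.** Section 4.1 lists the four arms and ends "and (4)Virtual/Telephone, stratified by genetic group". Section 6.4 says "Subjects will be randomized 1:1:1:1 into each of the 4 factorial-design groups" and does not mention strata. Section 9.2 gives the genetic mix of each arm: "divided between PD+gene+ (45%), PD+gene- (45%), and" 10% PD-gene+.

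**Baseline data.** The Schedule of Events (1.3) and the Schedule of Activities (12.1) place GKS, GDS, STAI and PDQ-39 at Visit 1, with GKS explicitly before counselling. IES-R is first taken at Visit 3. GCSS is first taken at Visit 1, after pre-test counselling.

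**Models.** Section 9.4.1 sets the covariate rule: "Covariates will be determined based on their significance as independent predictors of outcome, although age and sex will be included in all models". It gives no candidate list and no level specific to selection. Section 9.4.2, written for IES-R, says "A linear regression model accounting for baseline differences in age, sex, and other relevant covariates will be used". Section 9.4.7 says "All Primary and Secondary endpoints will be compared using age and sex as covariates in each multivariate model" and adds a comparison of PD and gene groups, which is a subgroup analysis. Section 9.4.5 compares the arms on baseline characteristics, including the secondary scales, but does not say that the models will adjust for them.

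**The concern.** A stratification factor is normally a fixed term in the primary model, and so is a baseline score expected to predict the outcome. Here both may enter only if they prove significant against the outcome. Three things could be at stake:

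- The content of the primary model is unknown until the outcome data are examined. Several covariate sets fit the text, which leaves room for analyst choice.
- If the stratum drops out, the model's standard error ignores balance that the design built in, and is too large.
- If a prognostic baseline score drops out, precision that has already been paid for is lost.

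The plan does not exclude these variables. It makes their entry conditional.

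**Working it through.** **Inputs from the documents.** 320 randomised 1:1:1:1; attrition 15–20%; alpha 0.05 and power 80%; limit 0.5 SD (Section 9.2, for IES-R only); strata 45/45/10. The first hypothesis in Section 9.1 compares factor levels (GKS "will not differ between virtual pre-test genetic counseling and IMAGINE-PD methods"), so with 20% attrition the comparison has 320 × 0.8 / 2 = 128 per side.

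**Assumptions.** The documents give neither the variance explained by genetic group (R²) nor the correlation of a baseline score with the outcome (r). I use R² = 0.02 and 0.10, and r = 0.3 and 0.5. Power and false-equivalence figures assume TOST, which the analysis section does not state.

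**1. The plan's own figure.** For TOST with a true difference of 0, n per group = 2 × ((1.645 + 1.282)/limit)². At 0.5, 0.75 and 1 SD this gives 68.5, 30.4 and 17.1. Divided by 0.85 for 15% attrition, these become 80.6, 35.8 and 20.2, against 80, 36 and 20 in Table 3. So TOST at one-sided 0.05 reproduces the per-group sizes and is a reasonable working assumption.

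**2. Stratum left out.** The standard error is overstated by 1/√(1 − R²): 1/√0.98 = 1.010 and 1/√0.90 = 1.054. With 55% carriers and 45% non-carriers, R² = 0.55 × 0.45 × D², so these values need a gap D of at least 0.28 and 0.64 SD.

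**3. Prognostic baseline score left out.** The standard error is valid, but the forgone factor is √(1 − r²): 0.954 at r = 0.3 and 0.866 at r = 0.5, that is reductions of 5% and 13%.

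**4. Power at 0.5 SD** (t quantiles):

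| Comparison | One-sided alpha | r = 0 | r = 0.3 | r = 0.5 |
|---|---|---|---|---|
| 128 per side | 0.05 | 98.1% | 98.9% | 99.7% |
| 128 per side | 0.05/3 = 0.0167 | 93.6% | 95.9% | 98.7% |
| 64 per side | 0.05 | 75.7% | 80.8% | 89.1% |

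The second row reflects Section 9.4.2 ("Bonferroni correction will be used to correct for multiple-testing comparisons"), assuming that three scales share the alpha. The third applies only if single arms (80 × 0.8 = 64) were compared, which is not how the Section 9.1 hypotheses read.

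**5. The selection rule applied once.** Simulation: 256 evaluable, 45/45/10 strata, 2×2 factorial, 20,000 replicates per scenario, true difference at the limit, selection at p < 0.05. With 3–5 candidates, the true standard error differs from the fixed model's by −0.2% to +0.1%, coverage is 94.7–95.1%, and false equivalence is 4.8–5.1% against a nominal 5%. A smaller run (4,000 replicates) with six irrelevant candidates gave 5.3–5.6% selected and 5.0–5.3% fixed. In its weak-predictor scenario (r = 0.2, carrier gap 0.25 SD) the stratum term was kept in only 45–48% of runs at 128 per side.

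**6. Upper bound for analyst choice.** If any covariate subset that shows equivalence may be reported, false equivalence is 5.9–6.1% with no prognostic baseline score, 6.9–7.2% at r = 0.3 and 7.7–8.6% at r = 0.5.

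**7. Cost of fixing the terms.** If every added covariate is irrelevant, the simulated standard error moves from 0.1260 to 0.1265: 0.1265/0.1260 = 1.004, a rise of about 0.4%.

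**The case against.** **The variables are not excluded.** Section 9.4.2 allows further covariates, Section 9.4.5 names baseline measures that could serve as candidates, and Section 9.4.7 gives genetic group a role. This stands as far as it goes. But the Section 9.4.5 list omits GKS and genetic group, and a comparison of groups is not an adjustment term.

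**The level is implied.** Section 9.4.1 sets 0.05, two-tailed, for inferential tests, so a 0.05 level for selection is the natural reading. That is fair, though it is not stated for selection.

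**The selection rule does little harm.** This stands in full. A reader might infer that choosing covariates by significance seriously inflates false equivalence, but the simulation does not show that. The figures in step 6 partly break the plan's own rule, because they count subsets that keep non-significant terms or drop significant ones. With the 0.05 rule kept and only the candidate list free (2,500 replicates, five candidates), false equivalence was 4.9%, 6.0% and 7.2% at r = 0, 0.3 and 0.5. Nothing in the documents suggests that a list would be chosen by result.

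**Lost precision is harmless for equivalence.** A reader might infer that a larger standard error can never favour an equivalence claim. That holds under TOST, which the analysis section does not state. If non-significance on a two-tailed test were read as no difference, lost precision would favour that conclusion.

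**Sections 4.1 and 6.4 conflict.** A reader might infer this, but Section 6.4 is only silent on stratification.

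**Conclusion.** The point holds as a minor improvement. No primary model commits to the stratum or to a baseline score, and model content depends on the outcome data. The two omissions differ in kind: leaving out the stratum makes the standard error somewhat too large, provided randomisation is stratified as Section 4.1 says, while leaving out a baseline score only forgoes precision. At the factor-level comparison the power gain is under 2 points without a Bonferroni correction and about 2 to 5 points with one. All sizes rest on assumed R² and r, and the power and error figures also rest on TOST at 0.5 SD. The false-equivalence range of about 6–9% is an upper bound under free choice by result and should not be quoted as the expected error. The main reason to change the text is that a fixed model removes that choice at almost no cost.

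**What to change.** Replace the significance rule in Section 9.4.1 with fixed models, before outcome data are examined:

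- **All three primary scales:** the counselling factor under test, the other counselling factor (given the factorial design), genetic group in its three categories, age and sex.
- **GKS:** add baseline GKS.
- **IES-R:** it has no baseline of its own, so add baseline STAI and GDS, the closest affective measures collected.
- **GCSS:** add no baseline score. Do not adjust for the Visit 1 GCSS, which follows the randomised pre-test counselling and which Section 9.1 also treats as an outcome.
- **Other covariates:** sensitivity analysis only.

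Add a cross-reference in Section 6.4 to the stratification stated in Section 4.1.

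Cost: one paragraph and one line, with no new data, visits or participants. IES-R needs the most terms: 2 degrees of freedom for genetic group and 2 for STAI and GDS, so 4, or 5 if the second counselling factor is not already in the model.
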